3.7 OTHER ANALYSES

3.7.1 PK analyses

The PK analyses will be produced only in the first step analysis (see [Section 3.8.2](#)).

A PK sub study is planned on 15 participants in primary population. Some supplementary time points were collected at D1 visit for these specific participants. The details of time points are presented in [Table 14](#).

Plasma and CSF venglustat concentrations will be summarized as per analysis window (see [Table 14](#)) and by theoretical time (Day 1 and Week 12) using the following descriptive stats: mean, geometric mean, median, standard deviation, coefficient of variation, minimum, and maximum.

PK samples collected outside of the sampling time window or PK samples collected as unscheduled samples will be classified as “undefined concentrations”. No descriptive statistics will be performed on these concentrations. Plasma venglustat PK parameters will be determined

using noncompartmental methods (when data permits) on Day 1 and Week 12 visits and summarized using descriptive statistics mentioned above. Plasma PK parameters will be estimated and summarized under the responsibility of Pharmacokinetics, Dynamics and Metabolism (PKDM) function, Sanofi.

The PK results will be presented separately in the primary and secondary population. For the secondary population an analysis according to the weight group at baseline will also be described.

All concentration values below the lower limit of quantitation (LLOQ) will be treated as zero in all summary statistics excepted for the geometric mean and associated coefficient of variation for which they will be considered as missing.

Mean values below lower limit of quantification (LLOQ) will be reported as LLOQ in the tables and not plotted in the figures if after C_{max} . Mean calculations and their associated statistics will be generated from unrounded numbers and may differ slightly from those values that would be determined using the rounded numbers displayed in the tables.

Plasma parameters during the primary analysis period will include, but may not be limited to:

- Day 1 (single dose administration): maximum plasma concentration observed (C_{max}), and in the PK sub study when data permits, maximum plasma concentration observed (C_{max}), time to reach C_{max} (t_{max}), and area under the plasma concentration versus time curve calculated using the trapezoidal method over a predefined time period (from time $t=0$ to 24 hours; AUC_{0-24}).
- Week 12: Maximum plasma concentration observed (C_{max}), time to reach C_{max} (t_{max}), and area under the plasma concentration versus time curve calculated using the trapezoidal method over a predefined time period (from time $t=0$ to 24 hours; AUC_{0-24}). In the PK sub study if data permits the accumulation ratio at Week 12/Day 1 will be presented for C_{max} and AUC_{0-24} (individual listings and descriptive statistics).
- Week 26: C_{trough} and C_{max} (such that C_{max} : Venglustat concentration sample taken 2 to 4 hours after IMP administration and - C_{trough} : Venglustat concentration sample taken just prior to IMP administration).
- Week 52: C_{trough} and C_{max} (such that C_{max} : Venglustat concentration sample taken 2 to 4 hours after IMP administration and - C_{trough} : Venglustat concentration sample taken just prior to IMP administration).
- Week 104: C_{trough} (such that C_{trough} : Venglustat concentration sample taken just prior to IMP administration).

Cerebrospinal fluid parameters during the primary analysis period will include:

- Week 104: predose concentration.

3.7.2 Pharmacodynamic analyses

In the first step analysis for the secondary population, the pharmacodynamic endpoint correspond to the primary endpoint and is described in [Section 3.2.4](#).

In the first step analysis for the primary population, the CSF GM2 parameter correspond to the primary and secondary endpoint. It is described in [Section 3.2.1](#) and [Section 3.3.1.2.1](#).

In the second step analysis for the secondary population, plasma samples for GL-1 and other biomarkers according to the disease (see [Section 1.2](#)) will be summarized on the PD population.

Plasma samples for GL-1, GM2 and CSF sample for GL-1 will be summarized on the pharmacodynamics primary population.

The CSF sample is only available in the primary analysis period. So, the measurement in CSF will be presented only in first step analysis.

Exploratory endpoints include percent change in:

- GL-1 from baseline to Week 104 (primary population in CSF and Plasma sample).
- GM2 from baseline to Week 104 (primary population in Plasma sample).
- GL-1 from baseline to Week 208 (primary and secondary population in Plasma sample).
- GM2 from baseline to Week 208 (primary population and secondary if applicable in Plasma sample).
- GM1 or GM3 from baseline to Week 208 (secondary population when applicable in Plasma sample).

Additional plasma and CSF biomarkers that may include lipidomics, glycoprotein nonmetastatic protein B (gpNMB) and neurofilament will be summarized on the PD primary and secondary populations if any.

Each PD variable will be summarized using descriptive statistics at each time point, including assessment of observed values, change and percent change from baseline.

3.8 INTERIM AND FINAL ANALYSIS

3.8.1 Interim analysis

No interim analysis is planned.

3.8.2 Final analysis

The final analysis will be conducted in two steps:

First step: Primary analysis period:

- The analysis of the primary analysis period of the study will be conducted when all participants have completed the primary analysis period of the study. It will consist in the final analysis of the primary, secondary, and exploratory endpoints at 104 weeks. The analysis of the primary analysis period will be conducted when all participants have completed the Week 104 visit or have prematurely discontinued the study.

- The cut-off date for the first step analysis will be the date of the last visit of the last participant during the primary analysis period.
- The analysis of the primary analysis period of the study will include all data collected up to the Week 104 visit. Any data collected during the open-label extension treatment period will not be included in this first step analysis.
- In order to further document safety for regulatory purpose, an overview of adverse events occurring during the open-label extension, up to the cut-off date of the primary analysis period will be provided.

Second step: analysis of the open-label extension treatment period:

- The analysis of the open-label extension treatment period of the study will be conducted when all participants have completed the Week 208 visit and safety follow up visit or have prematurely discontinued the study.

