3 STATISTICAL ANALYSES

3.1 GENERAL CONSIDERATIONS

Statistical significance for comparison between venglustat and placebo will be assessed at the Type I error rate of 0.05 one sided. Although a typical criterion for concluding that a trial is positive is a p-value of <0.05 two-sided, a higher Type I error rate of 0.05 one-sided was selected due to the rarity of late-onset GM2 gangliosidosis, the seriousness of this disease and lack of available therapy, as per Food and Drug Administration (FDA) draft guidance (1).

In general, continuous data will be summarized using the number of observations available, mean, standard deviation (SD), median, [Q1, Q3] minimum, and maximum. Categorical and ordinal data will be summarized using the count and percentage of participants.

The baseline value is defined as the last available value before or equal to the first dose of investigational medicinal product (IMP) date in the primary analysis period. For participants randomized but not exposed, the baseline value is defined as the last available value before or equal to the date of randomization.

Unless otherwise specified, analyses will be performed by intervention group (and overall for baseline and demographics characteristics).

The two analysis periods described below are defined:

- The **primary analysis period** is defined as the period starting at the date of signed informed consent, and ending at the end of Week 104 visit, or the day before the first IMP OLE administration (whichever comes last). For participants not exposed to IMP in the OLE, the primary analysis period ends at the date of end of study.
- The **OLE period** (only for participants exposed to IMP in the OLE) is defined as the period starting the day after the end of primary analysis period, until the end of the study.

Within each analysis period, the following observation periods are defined:

During the **primary analysis period** (as defined above), the following observation periods are defined:

- The **pre-treatment period** is defined as the time from the signed informed consent date up to the first IMP administration.
- The **treatment-emergent (TE) period** is defined as the time from the first IMP administration to the last administration of IMP during the primary analysis period +6 weeks (including any temporary treatment discontinuation period, if any) or the end of the primary analysis period (whichever comes first).

The TE period includes the following 2 periods:

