3.6 SAFETY ANALYSES

All safety analyses will be performed on the safety populations as defined in [Section 2](#) for the two steps analysis, unless otherwise specified, using the following common rules:

- The analysis of the safety variables will be essentially descriptive, and no testing is planned.
- Safety data in participants who do not belong to the safety population (eg, exposed but not randomized) will be provided separately if any.

In the first step analysis, safety data will be presented for the following period:

- Safety analysis of the primary analysis period. This analysis will present safety data collected during the primary analysis period (as defined in [Section 3.1](#)). Safety analyses will present safety data in the following arms:
 - Primary population – Placebo: participants from the primary population, having received placebo during the primary analysis period.
 - Primary population – Venglustat: participants from the primary population, having received venglustat during the primary analysis period.
 - Secondary population – Venglustat: participants from the secondary population, having received venglustat during the primary analysis period.

In the second step analysis, safety data will be presented separately for the two following periods:

- Safety analysis of the OLE period. This analysis will present safety data collected during the OLE period (as defined in [Section 3.1](#)). Only participants having received venglustat during the OLE period will be included in this analysis. Safety analyses will present safety data from the following groups:
 - Primary population - Delayed venglustat: participants from the primary population, having received placebo during the primary analysis period, then having received venglustat during the OLE period.
 - Primary population - Early venglustat: participants from the primary population, having received venglustat during the primary analysis period, then having continued to receive venglustat during the OLE period.

- Primary population - All venglustat: all participants from the primary population having received venglustat during the OLE period.
- Secondary population – Venglustat: participants from the secondary population having received venglustat during the OLE period.

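### SAP 3.8.2 ends first-step data at the Week 104 visit, while SAP 3.1 and 3.6 run first-step safety later for participants who skip the open-label extension (OLE) or start it late

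*SAP*

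**What the plan says.** SAP 3.8.2 sets the content of the first step: "The analysis of the primary analysis period of the study will include all data collected up to the Week 104 visit". It then excludes data from the OLE treatment period. On timing it says two things. The analysis is run when everyone has completed the primary analysis period, and also when all participants have "completed the Week 104 visit or have prematurely discontinued the study". The cut-off is "the date of the last visit of the last participant during the primary analysis period".

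SAP 3.1 defines the primary analysis period as "ending at the end of Week 104 visit, or the day before the first IMP OLE administration (whichever comes last"), and adds: "For participants not exposed to IMP in the OLE, the primary analysis period ends at the date of end of study". Its treatment-emergent window runs "to the last administration of IMP during the primary analysis period +6 weeks", or to the end of the primary analysis period if that comes sooner. Any remaining time in the period is post-treatment.

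SAP 3.6 describes the first-step safety analysis, which has a placebo arm, in these words: "This analysis will present safety data collected during the primary analysis period", with a reference back to 3.1. For the second-step OLE safety analysis it says: "Only participants having received venglustat during the OLE period will be included in this analysis".

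**The concern.** The SAP has two end points for the same first-step safety data. They differ for two groups: participants who complete Week 104 and do not enter the OLE, and those whose first OLE dose comes some time after the Week 104 visit. Adverse events in that interval are collected by design. Protocol 1.1 and 4.1 schedule a safety visit 6 weeks after Week 104 for completers who do not continue, and Protocol 8.3.1 collects events up to the 6-week follow-up visit.

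At stake is part of the placebo-controlled safety comparison. For these participants the interval contains the residual treatment period that the SAP itself defines. It also follows the Week 104 lumbar puncture, which the Schedule of Activities asks to be done after the other assessments if possible. If the conflict is left open, someone will have to choose between two treatment-emergent tables, possibly after unblinding.

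**Working it through.** There is no plan figure to reproduce. The check sets the rules side by side and then follows an adverse event that starts after the Week 104 visit.

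**Step 1. Where first-step safety data end.** The Week 104 target is Day 728 (SAP 5.4, Table 13). Six weeks later is 728 + 42 = Day 770.

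| Participant | SAP 3.8.2, read literally | SAP 3.1 with 3.6 |
|---|---|---|
| Completes Week 104, no OLE dose | Week 104 visit, about Day 728 | End of study; follow-up visit at about Day 770 |
| Completes Week 104, delayed OLE start | Week 104 visit | Day before first OLE dose |
| OLE dose on the day after Visit 7 (usual case, Protocol 1.3) | Week 104 visit | Same; no gap |

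Delayed entry is open to those who completed within 3 months before local approval of amended protocol 4 (Protocol 4.1). The exact length of the gap is not stated.

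**Step 2. Where such an event is reported if 3.8.2 governs.**

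- First-step safety tables: no, because it falls after the Week 104 visit.
- First-step overview of OLE events (last bullet of the first step in 3.8.2): no. Under 3.1 the OLE period starts only after the primary analysis period ends, so this is not an OLE event.
- Second-step OLE safety analysis: no. A participant without an OLE dose is excluded, and for a late starter the event precedes the OLE period.
- Second-step overall venglustat analysis, which runs from first to last venglustat intake plus 6 weeks: yes for the venglustat arm. A non-continuing participant is covered for 6 weeks after the last dose. A late starter on venglustat is covered throughout the gap. There is no placebo group, and a placebo participant's time before a first venglustat dose is outside the window.

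Placebo events in the interval therefore appear nowhere, and venglustat events reappear only without a comparator.

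**Step 3. Where it is reported if 3.6 governs.** It is in the first step, in both arms. It counts as treatment-emergent within 6 weeks of the last dose, and as post-treatment after that. Table 10 plans a post-treatment overview, and SAP 3.6.2 plans a summary of deaths in both periods.

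**Step 4. Timing.** The two triggers in 3.8.2 coincide for a participant who starts the OLE the day after Visit 7. For a completer who does not enter the OLE, they differ by about 6 weeks (Day 728 against Day 770). The second-step trigger names the safety follow-up visit and the first-step trigger does not. A lock at the last Week 104 visit could therefore come before data that 3.6 calls for.

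**Step 5. Weight of one event.** With the planned 19 placebo and 38 venglustat participants (SAP 4), one more participant with an event moves incidence by 1/19 = 5.3 percentage points on placebo and 1/38 = 2.6 on venglustat.

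**The case against.** The strongest reply is that 3.6 is the specific rule for safety. It refers explicitly to 3.1 and lists a placebo arm, so late placebo events are already planned for the first step. The cut-off bullet in 3.8.2 also speaks of the primary analysis period, and its Week 104 sentence can be read as doing no more than separating the 104-week analysis from the OLE. Completers enter the OLE automatically and normally start the next day. Delayed entry was a transitional arrangement tied to one amendment.

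Much of this stands. A reader might infer from 3.8.2 that the SAP plainly discards these events. The documents do not support that: they hold two conflicting rules, and one of them keeps the events. A reader might also infer that the comparison loses the residual treatment period in general. It does not. Participants who stop treatment well before Week 104 have their 6-week window before that visit under either rule.

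The reply does not remove the conflict. The sentence in 3.8.2 covers all data and makes no exception for safety, and the SAP does not say which section prevails. The second trigger sentence allows the analysis at Week 104 even when 3.6 decides the content.

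**Conclusion.** SAP 3.8.2 is inconsistent with SAP 3.1 and 3.6 on where first-step safety data end, and inconsistent within itself on when the first step may run. The loss of events from the controlled comparison is conditional on 3.8.2 being applied as written. The risk of locking before the last follow-up visit exists under either reading.

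The effect is confined to safety data in completers who do not enter the OLE or enter it late, and in participants who stop treatment within 6 weeks before Week 104 and are followed beyond that visit. The co-primary and secondary efficacy endpoints are unaffected. The documents do not say how many participants are involved; automatic OLE entry suggests few. It would be tempting to assume a share not entering the OLE and convert it to lost participant-time. That is not supported: no such share is given, and those who stop treatment early cannot enter the OLE (Protocol 4.1) yet mostly lose no treatment-emergent time. The per-event percentages assume that the planned arm sizes are reached.

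The point is worth correcting before unblinding, because the placebo arm is small and the correction is cheap.

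**What to change.** In SAP 3.8.2, replace the Week 104 sentence with one that separates the data types. The first step includes efficacy and PD data up to the Week 104 visit, and all safety data collected during the primary analysis period as defined in Section 3.1. State that this covers the 6-week follow-up of participants not entering the OLE and any interval before a delayed first OLE dose.

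Replace the two trigger sentences with one, and word the cut-off to match, so that the first step waits for the 6-week follow-up visits of participants not entering the OLE. Protocol 9.5 carries the same pair of trigger sentences, so the SAP should say which applies.

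The cost is SAP wording, plus a possible delay of up to about 6 weeks to the first-step lock if one of the last participants to reach Week 104 does not continue. No additional data collection is needed.

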3.9 CHANGES TO PROTOCOL-PLANNED ANALYSES

This section summarizes major statistical changes in the protocol amendment(s).

[figure not shown]
[figure not shown]
[figure not shown]
Table 12 - Major statistical changes in protocol amendment(s)

Amendment Number	Approval Date	Changes	Rationale
01	05-Nov-2019	Added a paragraph regarding power for the co-primary endpoint of percent change in CSF GM2 from baseline to Week 104.	Clarify the power on the co-primary endpoint.
04	20-Apr-2022	Added a 2-step analysis for the study, first step for the final analysis of the primary analysis period and second step for the final analysis of the OLE period.	Addition of OLE to the study.

4 SAMPLE SIZE DETERMINATION

In the primary population, approximately 57 participants will be randomly assigned with a 2:1 randomization ratio to venglustat (n=38) or placebo (n=19). This sample size will provide approximately 80% power to detect a difference between venglustat and placebo with regards to the primary efficacy endpoint of annualized rate of change in 9-HPT.

Sample size and power calculations were based on simulations (see [Section 5.6.3](#) for details).

5 SUPPORTING DOCUMENTATION

5.1 APPENDIX 1 LIST OF ABBREVIATIONS

25-FWT:	25-foot walk test
9-HPT:	9-hole peg test
AE:	adverse event
AESI:	adverse event of special interest
ALT:	alanine transaminase
ANCOVA:	analysis of covariance
AUC ₀₋₂₄ :	area under the plasma concentration versus time curve calculated using the trapezoidal method over a predefined time period (0 to 24 hours)
C _{max} :	maximum plasma concentration observed
CRF:	electronic case report form
CSF:	cerebrospinal fluid
DMC:	data monitoring committee
ECG:	electrocardiogram
FARS:	Friedreich's ataxia rating scale
FARS-neuro:	neurological examination of FARS
FDA:	Food and Drug Administration
GL-1:	glucosylceramide
GM3:	monosialodihexosylganglioside
HGLT:	high level group term
HLT:	high level term
ICF:	inform consent form
IMP:	investigational medicinal product
IRT:	interactive response technology
IWPM:	intelligible words per minute
LLOQ:	lower limit of quantification
LLT:	lower level term
MedDRA:	Mecical Dictionary for Regulatory Activities
MMRM:	mixed model with repeated measures
MSFC:	multiple sclerosis functional composite
OLE:	open-label extension
PCSA:	potentially clinically significant abnormality
PD:	pharmacodynamic

PK: pharmacokinetic
PKDM: pharmacokinetics dynamics and metabolism
PRO: patient reported outcome

PT: preferred term
SAE: serious adverse event
SAP: statistical analysis plan
SD: standard deviation
SOC: system organ class
TE: treatment-emergent
TEAE: treatment-emergent adverse event
 t_{max} : time to reach maximum plasma concentration

ULOQ: upper limit of quantification
WHO-DD: World Health Organization-drug dictionary

5.2 APPENDIX 2 PARTICIPANT DISPOSITIONS

The number (%) of participants included in each of the analysis populations listed in [Table 3](#) will be summarized. The reasons for exclusion from the population without trial impact (disruption) due to COVID-19 will be also summarized.

Screen failures are defined as participants who consent to participate in the study but are not subsequently randomized. The number (%) of screen failures and reasons for screen failures will be provided in the screened population.

The number (%) of participants in the following categories will be provided:

- Randomized participants.
- Randomized but not exposed participants.
- Randomized and exposed participants.
- Participants who completed the study treatment period as per protocol.
- Participants who did not complete the study treatment period as per protocol and main reason for permanent intervention discontinuation.
- Participants who completed the study period as per protocol.
- Participants who did not complete the study period as per protocol and main reason for study discontinuation.

The number (%) of exposed and not randomized participants will also be summarized.

In addition, the number (%) of participants screened, screened-failed, randomized, with permanent intervention discontinuation and with early study discontinuation will be provided by country and site.

Protocol deviations

Critical and major protocol deviations (automatic or manual) will be summarized in the randomized population as well as displayed separately according to their relation to COVID-19.

Disposition by visit

Participant disposition by visit will be provided according to trial impact (disruption) due to COVID-19, as reported in CRF.

